In addition to the heart and lung alterations that occur in breath hold divers outlined above, it is also known that pulmonary arterial pressure increases after SCUBA diving, but returns to normal within a few hours. The mechanisms responsible for the increase in pulmonary arterial pressure are unknown, but are independent of hypoxia. Thus, investigating the relationship between IPAVA, PFO and SCUBA diving-induced increases in pulmonary arterial pressures offers an additional avenue for understanding pulmonary arterial hypertension susceptibility. Although it is unknown why pulmonary arterial pressure increases with SCUBA diving, it is known that pulmonary hypertension may contribute to right heart dysfunction and pulmonary edema (lung water accumulation) that can occur in subjects who are swimming and/or SCUBA diving. Prevention of increased pulmonary arterial pressures during and/or after a dive may help to prevent excessive right heart dysfunction and pulmonary edema. Thus, **Objective #4** will quantify pulmonary arterial pressure and right heart function and investigate their relationships with PFO and IPAVA blood flow, pre- and post-SCUBA diving. **Objective #5** will quantify the effect of sildenafil (post dive) on pulmonary arterial pressure and right heart function and will determine if it alters the relationship with IPAVA and PFO blood flow, pre- and post-SCUBA diving.

In summary, we propose to study elite Croatian breath-hold and SCUBA divers. We will quantify breath-hold hypoxia- and SCUBA diving-induced pulmonary hypertension and right heart function to investigate the relationships between PFO and IPAVA blood flow. We will use a placebo-controlled intervention (sildenafil) to

reduce pulmonary arterial pressure in these subjects to examine the impact of the change in pressure (or absence of change) on the relationships determined above.

B. Specific Aims/Study Objectives

The overarching goal of this study is to examine cardiopulmonary and respiratory physiology in breath hold and SCUBA divers.

In breath hold divers we will:

- 1) Quantify pulmonary arterial pressure and right heart function and determine their relationships with PFO and IPAVA blood flow in elite breath-hold divers. We hypothesize:
 - a. PFO- subjects with high pulmonary arterial pressures will have low IPAVA blood flow, and vice versa.
 - b. PFO+ subjects will have high pulmonary arterial pressures independent of blood flow through IPAVA.

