Subjects will ingest a placebo or sildenafil (50 mg oral) and wait until peak effect (~1hr), and then breathe low oxygen and high carbon dioxide gas mixtures that mimic blood gases during a breath hold with measure of cardiac output, pulmonary pressure and left and right heart function measures made every 2 minutes and during the last minute of the subjects breath hold (based on the average length the subject reports to be able to hold their breath) (~1.5 hrs).

Visit 2 Overview: Subjects will ingest either a placebo or sildenafil (50mg, oral) (whatever they didn't take during visit 1) wait an hour for peak effect and then and then breathe low oxygen and high carbon dioxide gas mixtures that mimic blood gases during a breath hold, during which ultrasound measures of the heart and lungs will be made (~2 hrs)

Visit 2 Details:

The subjects will be instrumented with forehead oxygen saturation monitor, ECG and blood pressure cuffs and baseline ultrasound measures of cardiac output, pulmonary pressure and left and right heart function measures will be made before breath hold (30 min).

Subjects will ingest a placebo or sildenafil (50 mg oral) and wait until peak effect (~1hr), and then breathe low oxygen and high carbon dioxide gas mixtures that mimic blood gases during a breath hold with measure of cardiac output, pulmonary pressure and left and right heart function measures made every 2 minutes while the subjects are breathing low oxygen and high carbon dioxide gas mixtures (~10 minutes) that mimic blood gases during a breath hold, (based on the average length the subject reports to be able to hold their breath) (~1.5 hrs).

Experienced SCUBA Diving Subjects (Objectives 4 & 5)

Visit 1 Overview: Subject consent, screening, lung function and anthropometrics. Subjects will perform a dive and then post dive they will ingest either a placebo or sildenafil (50mg, oral), wait an hour for peak effect and then ultrasound measures of the heart and lungs will be made (~5 hrs). Subjects will utilize SCUBA equipment owned and maintained by the Croatian Navy.

Visit 1 Details:

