Subjects will undergo informed consent, fill out health history questionnaire (~45 min. Five to 10 hours prior to the dive start time, subjects will be given a telemetric pill to swallow prior to testing. The telemetric pill will be used to measure pre- and post-dive core temperatures in the divers. If the subjects do not swallow the core temperature pill, they will be asked to insert the pill as a suppository the morning of testing.

Subjects will be comprehensively screened for any cardiac abnormalities. Amount of blood flow travelling through the PFO and IPAVA will be graded using saline contrast echocardiography while the subject is breathing room air (PFO and IPAVA blood flow) and breathing 100% O₂ (PFO blood flow only). Pulmonary artery pressure, cardiac output and right and left heart function will also be measured using ultrasound. Subjects will undergo an intravenous blood draw. We will take 21 mL (~2 Tablespoons) of IV blood (~1.25 hrs)

Subjects will perform pulmonary function tests. (15min)

Subjects will perform dives to depths up to 30 meters and lasting up to 75 minutes with decompression profiles determined using V-planner software according to the varying permeability model (~1.25 hrs). The Dive Master will ensure that all divers have a 'dive buddy', a SCUBA-certified individual of similar or greater experience than the subject. The subject will be encouraged to identify a 'dive buddy' to accompany them, but in the event that the subject is unable to secure a 'dive buddy', the Dive Master will ensure that the subject has a 'dive buddy' for the dive.

Subjects will ingest a placebo or sildenafil (50 mg oral) upon resurfacing and coming aboard dry land. During the hour wait until peak effect, the subjects will be instrumented with a forehead oxygen saturation monitor, ECG and blood pressure cuffs. Pulmonary artery pressure, cardiac output and right and left heart function will also be measured using ultrasound. In addition, a post-dive venous blood draw of 21 mL will be taken. This blood draw will occur 1 hour after placebo or sildenafil administration. (~1.5 hrs).

Visit 2 Overview: Subjects will perform a dive and then post dive they will ingest either a placebo or sildenafil (50mg, oral), wait an hour for peak effect and then ultrasound measures of the heart and lungs will be made (~3 hrs). Subjects will utilize SCUBA equipment owned and maintained by the Croatian Navy.

Visit 2 Details:

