Five to 10 hours prior to the dive start time, subjects will be given a telemetric pill to swallow prior to testing. The telemetric pill will be used to measure pre- and post-dive core temperatures in the divers. If the subjects do not swallow the core temperature pill, they will be asked to insert the pill as a suppository the morning of testing. Prior to the dive, subjects will have 21 mL of venous blood drawn. After, subjects will perform dives to depths up to 30 meters and lasting up to 75 minutes with decompression profiles determined using V-planner software according to the varying permeability model (~1.25 hrs). The Dive Master will ensure that all divers have a 'dive buddy', a SCUBA-certified individual of similar or greater experience than the subject. The subject will be encouraged to identify a 'dive buddy' to accompany them, but in the event that the subject is unable to secure a 'dive buddy', the Dive Master will ensure that the subject has a 'dive buddy' for the dive. Subjects will utilize SCUBA equipment owned and maintained by the Croatian Navy.

Subjects will ingest a placebo or sildenafil (50 mg oral) upon resurfacing and coming aboard dry land. During the hour wait until peak effect, the subjects will be instrumented with forehead oxygen saturation monitor, ECG, and blood pressure cuffs. Pulmonary artery pressure, cardiac output and right and left heart function will also be measured using ultrasound. In addition, a post-dive venous blood draw of 21 mL will be taken. This blood draw will occur 1 hour after placebo or sildenafil administration. (~1.5 hrs).

Description of Data Collection Procedures

- **Comprehensive ultrasound screening** (Day 1 for Breath Hold and SCUBA divers):

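### Is the post-dive ultrasound in the SCUBA arm taken before sildenafil reaches its peak effect?

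*Combined protocol and SAP*

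**What the plan says.** Section C describes each SCUBA visit twice, first as an overview and then in detail.

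- **Visit 1 Overview:** after the dive and the tablet, subjects "wait an hour for peak effect and then ultrasound measures of the heart and lungs will be made (~5 hrs").
- **Visit 2 Overview:** the same order, "wait an hour for peak effect and then ultrasound measures of the heart and lungs will be made (~3 hrs").
- **Visit 1 Details:** the tablet is given on return to dry land, and then "During the hour wait until peak effect, the subjects will be instrumented with a forehead oxygen saturation monitor, ECG and blood pressure cuffs". The next sentence reads "Pulmonary artery pressure, cardiac output and right and left heart function will also be measured using ultrasound". It is followed by the post-dive blood draw, which has its own time and closes the block: "This blood draw will occur 1 hour after placebo or sildenafil administration. (~1.5 hrs").
- **Visit 2 Details:** the same sequence, in nearly the same words.
- **SCUBA diving entry under Description of Data Collection Procedures:** instrumentation is the only activity listed for the hour's wait. The ultrasound is not mentioned, and the block is again about 1.5 h.

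Section A adds that "pulmonary arterial pressure increases after SCUBA diving, but returns to normal within a few hours". Section D names pulmonary artery systolic pressure as one of the primary outcome variables.

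**The concern.** In the details, the ultrasound sentence comes straight after the one about the hour's wait and contains the word also. A reader can carry the wait over the full stop and conclude that the scan is done while the drug effect is still building. The blood draw has a post-dose time and the scan has none, which seems to support that reading.

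Pulmonary artery systolic pressure is a primary outcome, and Objective 5 is the effect of sildenafil on it after a dive. Two things change during the window: the drug effect rises toward the plan's own one-hour peak, and the dive-induced pressure rise is subsiding. A scan part-way through the wait would tend to understate the drug effect. Scans at different times on a diver's two visits would mix drug effect with recovery time. A weak effect in divers with a PFO could then be mistaken for the reduced response that hypothesis 5b predicts.

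**Working it through.** **1. The passages side by side.**

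| Place | Activity during the wait | Time of ultrasound |
|---|---|---|
| Visit 1 Overview | none listed | after the hour |
| Visit 2 Overview | none listed | after the hour |
| Visit 1 Details | instrumentation | not stated |
| Visit 2 Details | instrumentation | not stated |
| Procedures, SCUBA diving | instrumentation | ultrasound not mentioned |

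Two entries give a time, and they agree. None gives a competing time. The ultrasound sentence in the Visit 1 details also appears, word for word, in the pre-dive screening paragraph of the same visit. There, the word also plainly has nothing to do with any wait. It adds an item to a list and does not set a time.

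**2. The plan's own durations.** The Visit 1 details give consent and questionnaire 0.75 h, screening and blood draw 1.25 h, lung function 0.25 h, dive 1.25 h and post-dose block 1.5 h.

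0.75 + 1.25 + 0.25 + 1.25 + 1.5 = 5.0 h, which reproduces the 5 h in the overview.

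For Visit 2, the timed components are the dive and the post-dose block: 1.25 + 1.5 = 2.75 h of the stated 3 h. That leaves 0.25 h for the untimed pre-dive blood draw and preparation.

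**3. Room after the wait.** Post-dose block minus wait: 1.5 − 1.0 = 0.5 h. The breath-hold visits have a block of the same length, about 1.5 h, in which the order is explicit: tablet, one hour's wait, then gas breathing with ultrasound. The durations therefore fit a scan after the wait. They do not prove it, because instrumentation and ultrasound are not timed separately.

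**4. The clock from surfacing.** The tablet is given once the diver has surfaced and is on dry land. A scan that follows a one-hour wait from the tablet is therefore also roughly tied to surfacing, on both visits.

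**5. What an early scan would cost, as an illustration.** Suppose that a scan sees a fraction *f* of the peak effect, and that power is 0.80 at n = 10 in a two-sided paired t test at 0.05. Solving for the standardized paired effect gives dz = 0.996. With dz × *f* in the noncentral t distribution:

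| n | *f* = 0.75 | *f* = 0.50 | *f* = 0.25 |
|---|---|---|---|
| 10 | 0.56 | 0.29 | 0.11 |
| 12 | 0.66 | 0.35 | 0.12 |
| 25 | 0.95 | 0.67 | 0.22 |

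The rows n = 10 and n = 12 correspond to single sex-by-PFO cells. The row n = 25 corresponds to one PFO group with the sexes pooled.

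The arithmetic is right, but its inputs are not in the documents. No time course of drug effect is given, so *f* is an assumption. No standard deviation or correlation is given, so dz is solved backward from the power. Section D also does not tie its 25% pressure difference to the comparison of sildenafil with placebo.

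**The case for a change.** The strongest opposing case is that the details are the working text and that they omit the overview's explicit order. The breath-hold details keep that order, so its absence from the SCUBA details could be deliberate. A sonographer working from the details alone could scan at 15 minutes on one visit and 75 on the other without departing from the page. Stating the order would take one sentence per visit.

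Part of this stands. The details give the post-dive scan no post-dose time, although they give the blood draw one, and the placement of the sentence allows an early reading. It would be good practice to log minutes from surfacing and from ingestion.

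The rest does not stand. The SCUBA details do not appear alone. Each follows an overview that states the order, and a detail that is silent on a point is filled in by the overview. The argument about hypothesis 5b also fails. An early scan would weaken the measured effect in divers with and without a PFO alike and would shrink the difference between them. It would not by itself produce the predicted pattern.

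**Conclusion.** The concern does not hold as a contradiction and calls for no change to the plan. The documents show one untimed sentence in each SCUBA details section, beside two overviews that both put the scan after the hour. The block length, the 5 h total for Visit 1 and dosing on surfacing all fit that order. This is a drafting gap that a team following section C as a whole would fill correctly, and rewording would only repeat what the overviews already say.

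This rests on one assumption: that staff read the overview and the details together. If scans had in fact been made during the wait, the loss could matter, but its size cannot be derived from the documents. The power figures above show only how such a loss would scale under an assumed *f*.

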- **Intravenous Catheter (IV) and blood draw** (Days 1 & 2 for Breath Hold and SCUBA divers): We will place a 20-22 gauge (small diameter) IV into a vein in the subject's arm that will be used for the rapid injection of the agitated sterile saline for TTSCE. This catheter will also be used to measure serum inflammatory mediators. Blood will be centrifuged and de-identified serum stored at -80°C until assayed by ELISA kit. For the breath hold dive arms, blood will be drawn once on the first visit pre-breath hold (21 mL). For the SCUBA arm, blood will be drawn pre- and post-dive for both visits (21 mL per blood draw x4 blood draws). Total IV blood draw is therefore approximately 84 mL for SCUBA subjects.

- **Breathing low oxygen and high carbon dioxide** (hypercapnic hypoxia) to mimic breath hold (Days 1 & 2, breath hold and breath hold control subjects only):

Subjects will take either sildenafil or a placebo, and will be instrumented during the ~1 hour wait till peak effect. After being instrumented with ECG, forehead saturation and blood pressure monitoring equipment, subjects will breathe room air for 5-10 minutes to measure baseline breathing. During the first 5 minutes of the hypercapnic hypoxic conditions, subjects will breathe room air through a 2-way non-rebreathing Hans Rudolph mouthpiece. During the resting period end tidal (expired) Oxygen will be clamped at 100 mm Hg, while end tidal (expired) carbon dioxide will be maintained at resting levels (~30-40 mm Hg). Upon completion of the baseline measurements, end tidal carbon dioxide will be increased while end tidal oxygen will be reduced.

The values for oxygen and carbon dioxide for breath hold divers will be changed to 45-50 mm Hg CO2 and 50-60 mm Hg O2 and held at this level for approximately 5 minutes while ultrasound measures are made, then subsequently changed to 55-60 mm Hg CO2 and 30-40 mm Hg O2 and held at this level for approximately 5 minutes, while ultrasound measures are made. These values of oxygen and carbon dioxide were chosen based on previous values published in breath hold divers by my collaborating investigator [name] (Willie et al., J Cereb Blood Flow & Metab 2015).

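### Does SCUBA Visit 2 need a pre-dive pressure and heart-function ultrasound to match the one at Visit 1?

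*Combined protocol and SAP*

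**What the plan says.** Section C, under Experienced SCUBA Diving Subjects, lists an ultrasound of pressure, cardiac output and heart function at Visit 1 screening, before the dive: "Pulmonary artery pressure, cardiac output and right and left heart function will also be measured using ultrasound. Subjects will undergo an intravenous blood draw". A second scan follows the dive and the study drug.

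For Visit 2 the Details give only the pill and blood before the dive: "Prior to the dive, subjects will have 21 mL of venous blood drawn. After, subjects will perform dives to depths up to 30 meters". The scan comes after resurfacing and dosing. The Visit 2 Overview has the same order: "wait an hour for peak effect and then ultrasound measures of the heart and lungs will be made (~3 hrs". The comprehensive ultrasound screening entry is labelled "Day 1 for Breath Hold and SCUBA divers".

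Two other parts of Section C do repeat their baseline. The blood-draw entry says "For the SCUBA arm, blood will be drawn pre- and post-dive for both visits (21 mL per blood draw x4 blood draws". Breath-hold Visit 2 lists "baseline ultrasound measures of cardiac output, pulmonary pressure and left and right heart function measures will be made before breath hold (30 min".

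Section A states the aim as "We will quantify breath-hold hypoxia- and SCUBA diving-induced pulmonary hypertension and right heart function", and Objective #4 is to "investigate their relationships with PFO and IPAVA blood flow, pre- and post-SCUBA diving". Section D names pulmonary artery systolic pressure among the primary outcome variables.

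**The concern.** A primary outcome variable has fewer listed time points in the SCUBA arm (three) than the blood samples (four). The breath-hold arm repeats its baseline scan at Visit 2 and the SCUBA arm does not, and the plan gives no reason.

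With no Visit 2 baseline, a diver whose resting pressure differs between the two days cannot be told apart from a diver who responds differently to the second dive. Suppose the order of placebo and sildenafil is balanced and no visit effect is modelled. Half the undrugged before/after pairs then run from the Visit 1 baseline to the Visit 2 post-dive scan. A resting shift of d enters those 25 of 50 pairs and moves the mean undrugged dive change by 25d/50 = d/2. If a visit effect is modelled, the shift is removed, but the before/after change is then identified from Visit 1 alone.

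**Working it through.** **1. Is the scan really absent from the text?**

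- Listed pressure scans per diver: Visit 1 before, Visit 1 after, Visit 2 after. That is 3 of 4, or 50 same-day pairs out of a possible 100 in 50 divers.
- The stated times agree. Visit 1: 0.75 + 1.25 + 0.25 + 1.25 + 1.5 = 5.0 h, as stated. Visit 2: 1.25 + 1.5 = 2.75 h of about 3 h. That leaves about 15 minutes before the dive, against 30 minutes for the breath-hold baseline set.
- One caution: Section C schedules contrast echocardiography for SCUBA divers on both days, yet the Visit 2 Details do not mention it. The visit text is therefore incomplete. That entry names neither a pressure measure nor a time relative to the dive, so it does not supply the missing scan.

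**2. What would a fourth scan gain?**

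The documents give no SD, repeatability or SCUBA treatment order. Assumptions:

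- a crossover with 25 divers per order;
- visit-level variance 1, of which a share ρ is common to the two scans of one day;
- diver variance 10;
- one joint generalised least squares model with mean, visit, dive and treatment, using the Visit 1 scan in both designs.

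The fitted variance of the mean dive effect is reproduced by

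Var(dive) = 2(1 − ρ)/(same-day pairs) + Var(drug)/4,

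with 50 pairs for three scans and 100 for four. If true dive responses differ between divers with variance 1, add 1/50 = 0.02 and use the drug variance from that model.

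At ρ = 0, Var(drug) = 2/50 = 0.0400 in both designs:

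- three scans: 2/50 + 0.04/4 = 0.0500
- four scans: 2/100 + 0.04/4 = 0.0300, a cut of 40%

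| ρ | Dive, 3 → 4 scans | Cut | Cut, response variance 1 | Drug, 3 → 4 scans | Cut |
|---|---|---|---|---|---|
| 0 | 0.0500 → 0.0300 | 40% | 29% | 0.0400 → 0.0400 | 0% |
| 0.3 | 0.0376 → 0.0231 | 39% | 25% | 0.0385 → 0.0364 | 5% |
| 0.5 | 0.0287 → 0.0175 | 39% | 24% | 0.0350 → 0.0300 | 14% |
| 0.7 | 0.0189 → 0.0111 | 41% | 23% | 0.0277 → 0.0204 | 26% |

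Without a visit effect in the model, the dive-effect cut is 25 to 38%, or 17 to 22% with response variance 1. With the visit effect and larger response variance it is 16 to 22% (variance 2) and 10 to 15% (variance 4). A 20/30 order split, either way, gives 32 to 50%, or 17 to 33% with response variance 1.

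The resting shift itself would be estimated with SE √(2/50) = 0.20, so to within ±1.96 × 0.20 = ±0.39 visit-level SD. With three scans it cannot be separated from a visit-by-dive term: the five-parameter design has rank 4, against 5 with four scans.

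**3. Is the precision needed?**

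Section D judges 8 to 10 subjects per sex and group enough for a 25% pressure difference at 80% power and alpha 0.05. With no SD given, that figure cannot be reproduced, only back-solved. A two-sided paired t test needs a standardised difference of 1.16 (n = 8) or 1.00 (n = 10).

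Take the harder case, 1.00, and apply it to same-day pairs (assumption). The target in visit-level SD is 1.00 × √(2(1 − ρ)) = 1.41, 1.00 and 0.77 at ρ = 0, 0.5 and 0.7.

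The effect detectable with three scans and 50 divers is 2.80 × √Var(dive):

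- ρ = 0: 2.80 × √0.0500 = 0.63
- ρ = 0.5: 2.80 × √0.0287 = 0.47
- ρ = 0.7: 2.80 × √0.0189 = 0.39

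These are 44 to 50% of the target. For 25 divers of one sex, multiply by √2: 0.89, 0.67 and 0.55, still below target.

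**4. What would it cost?**

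0.5 h × 50 divers = 25 sonographer hours. Visit 2 becomes at least 2.75 + 0.5 = 3.25 h against about 3 h, and a sonographer is needed at the Navy site before the dive.

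**The case for a change.** The best case for a change is that the plan treats same-day baselines as worthwhile elsewhere and gives no reason to omit one for a primary outcome variable. The comparison above is fair to the existing design, because the three-scan model already uses the Visit 1 scan. Even so, the gain in the dive effect is material over most of the assumed range. The PFO+ versus PFO− difference in dive effect would gain 25 to 38% in variance (17 to 22% with response variance 1). The loss of a separate estimate of resting shift is a fact of the design, whatever correlation is assumed.

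All of that stands as a description of what a fourth scan would add. It does not show that the listed scans fail a stated aim. Objectives #4 and #5 ask for measurements before and after diving, and Visit 1 supplies them. They do not ask for two such pairs per diver. Hypotheses 4a to 4c concern pressure levels and their associations, not two same-day changes. The resting shift has no stated size or supporting evidence in the plan. The largest cuts come from unequal order groups or from every diver responding alike to a dive, which fits poorly with a study of why divers differ.

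**Conclusion.** The omission from the listed schedule is real; the need for a change is not. The post-dive sildenafil contrast is unaffected in validity, and the hypotheses can be tested on the three listed scans. A fourth would cut the variance of the mean dive effect by roughly 17 to 41% with equal order groups, with or without a modelled visit effect and for response variance 0 or 1. The cut is smaller if responses vary more. On the plan's own sizing that precision is not short, provided the back-solved standardised difference applies to same-day pairs. The price is an extra procedure in 50 divers and a longer visit at a field site, so leaving it out is a fair trade-off.

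The analysis gap is one an analyst fills sensibly: use the Visit 1 scan as baseline in a joint model with diver, visit, dive and treatment, and note in the report that about half the undrugged pairs span two days.

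Two facts limit the point further. Testing was set for summers 2019 and 2022 and this version is dated Sept 7, 2022, so the dives may already be done. Also, the SCUBA risk text in Section G describes a single dive, while Section C has a dive at each of two visits. Those passages must be reconciled in their own right, and with one dive per diver the question disappears.

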Taken together, during an elite breath-hold dive, where the level of oxygen decreases, we expect that pulmonary arterial pressures will increase as lung oxygen levels decrease, and the reduction in oxygen may be even lower in PFO+ subjects. Furthermore, as blood oxygen levels decrease, IPAVA blood flow will increase in some PFO- subjects thereby keeping pulmonary arterial pressures low in those individuals. Conversely, PFO+ subjects and those PFO- subjects with low levels of IPAVA blood flow would be expected to have the greatest pulmonary pressures. Whether or not this is true is unknown. Therefore, **Objective #1** will quantify pulmonary arterial pressure and right heart function and investigate their relationships with PFO and IPAVA blood flow in elite breath-hold divers while breathing concentrations of oxygen and carbon dioxide that mimic breath-hold-induced hypoxia [NOTE: it is not possible to image the heart during a breath hold because the fully inflated lung obstructs the ultrasound view of the heart]. **Objective #2** will use sildenafil, a drug that increases nitric oxide bioavailability to dilate lung blood vessels, to decrease pulmonary arterial pressure while breathing concentrations of oxygen and carbon dioxide that mimic breath-hold-induced hypoxia. We will quantify the effect of sildenafil on pulmonary arterial pressure and right heart function and will determine if it alters the relationship with IPAVA and PFO blood flow. As mentioned above, because those PFO+ subjects may have an exaggerated pulmonary vasoconstrictor response to hypoxia, sildenafil may be either less effective or ineffective in reducing the pulmonary arterial pressure in these subjects. **Objective #3** will compare the elite breath hold diver study data to data obtained in age, sex and PFO matched subjects who do not have extensive experience with breath hold diving. To do this control subjects will undergo the same procedures in **Objectives #1 & 2** above. These studies will also allow us to determine if there are differences in pulmonary vascular responses to hypoxia between those with and without breath hold diving experience.

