The values for oxygen and carbon dioxide for breath hold diver controls will be changed to 45-50 mm Hg CO2 and 60-70 mm Hg O2 and held at this level for approximately 5 minutes while ultrasound measures are made, then subsequently changed to 55-60 mm Hg CO2 and 40-50 mm Hg O2 and held at this level for approximately 5 minutes, while ultrasound measures are made. The values used for controls are based off of previous work by our group at altitude (Elliott et al., J Appl Physiol 2015). End tidal oxygen and carbon dioxide levels will be maintained using an end-tidal forcing (ETF) system, (Airforce, Endtidal Forcing System), (Querido et al., 2013; Bain et al., 2013; Foster et al., 2014). (~30 minutes for breathing gases and 1 hour of wait time for drug plasma levels to peak).

- **SCUBA diving** (Days 1 & 2, SCUBA subjects only): Subjects will perform dives to depths up to 30 meters and lasting up to 75 minutes with decompression profiles determined using V-planner software according to the varying permeability model. Subjects will be highly experienced divers. The Dive Master will ensure that all divers have a 'dive buddy', a SCUBA-certified individual of similar or greater experience than the subject.

The subject will be encouraged to identify a 'dive buddy' to accompany them, but in the event that the subject is unable to secure a 'dive buddy', the Dive Master will ensure that the subject has a 'dive buddy' for the dive. A 'Dive Buddy' will be required to provide evidence of appropriate SCUBA certification and ensure that they have not completed a recent dive. Subjects will ingest a placebo or sildenafil (50 mg oral) upon resurfacing and coming aboard dry land. During the hour wait until peak effect, the subjects will be instrumented with forehead saturation, ECG and blood pressure cuffs (~1.5 hrs).

Core Temperature: Core temperature (Tcore) will be measured using a Vital Sense Monitor and a telemetric pill (JonahTM ingestible temperature sensor, Mini Mitter Inc, Bend OR). The sterile telemetric pill will be activated by study staff then will be taken orally (with liquid) the 5-10 hours prior to testing or the volunteer will self-insert the pill into the rectum the morning of testing.

D. Research Population & Recruitment Methods & Compensation

Sample size, Population and Recruitment Methods:

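### Objective 3 promises a diver-control difference in the response to hypoxia, but every gas stage lowers O2 and raises CO2 together, so a difference cannot be attributed to low O2 alone

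*Combined protocol and SAP*

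**What the plan says.** Section A follows Objective 3 with an inferential claim: the studies will allow the team to "determine if there are differences in pulmonary vascular responses to hypoxia between those with and without breath hold diving experience". In explaining Objective 2 it also suggests that "those PFO+ subjects may have an exaggerated pulmonary vasoconstrictor response to hypoxia", as a reason why sildenafil may work less well in these subjects.

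The exposure is set out in Section C, Description of Data Collection Procedures, under the low-oxygen, high-carbon-dioxide breathing procedure. The procedure is openly labelled as combined: "hypercapnic hypoxia) to mimic breath hold". At rest, "end tidal (expired) Oxygen will be clamped at 100 mm Hg", and CO2 "will be maintained at resting levels (~30-40 mm Hg". Then "end tidal carbon dioxide will be increased while end tidal oxygen will be reduced". For divers the first stage is "changed to 45-50 mm Hg CO2 and 50-60 mm Hg O2", and the second is 55-60 mm Hg CO2 with 30-40 mm Hg O2. For controls the first stage is 45-50 mm Hg CO2 with 60-70 mm Hg O2, "then subsequently changed to 55-60 mm Hg CO2 and 40-50 mm Hg O2 and held at this level for approximately 5 minutes".

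The Visit 1 overview for breath-hold subjects (Section C) says that divers will receive less oxygen and more carbon dioxide than controls, and that the slopes of the responses will nevertheless be comparable. It does not say what the slopes are taken against.

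**The concern.** The claim attached to Objective 3 names hypoxia as the stimulus whose effect is compared between groups. The stimulus delivered always changes two gases at once. If divers and controls differ in how pulmonary pressure responds to CO2, that difference would be reported as a difference in the hypoxic response. The plan gives no argument that CO2 leaves pulmonary pressure unchanged, and it describes no analysis that would separate the gases. At stake is what the diver-control comparison may be said to show.

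**Working it through.** The plan has no figure of its own on this point; its sample-size statement (n = 8-10 per sex per group) does not bear on it. The check uses only the end-tidal targets in Section C.

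**Step 1: the stages side by side (O2 / CO2, mm Hg).**

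| Stage | Divers | Controls |
|---|---|---|
| Baseline | 100 / about 30-40 | 100 / about 30-40 |
| Stage 1 | 50-60 / 45-50 | 60-70 / 45-50 |
| Stage 2 | 30-40 / 55-60 | 40-50 / 55-60 |

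Stages with lowered O2 and resting CO2: 0 of 2 in each group. Stages with raised CO2 and normal O2: also none. The only other gases used are room air and 100% O2 at screening, and neither is hypoxic.

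**Step 2: how closely the gases move together.** Midpoints (O2, CO2):

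- Divers: (100, 35), (55, 47.5), (35, 57.5).
- Controls: (100, 35), (65, 47.5), (45, 57.5).

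With r = Sxy / √(Sxx·Syy):

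- Divers: -741.67 / √(2216.67 × 254.17) = -0.988.
- Controls: -625.0 / √(1550 × 254.17) = -0.996.

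Over the ends of the target ranges, r runs from about -0.80 to -1.00.

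**Step 3: does pooling the groups help?** At each stage the CO2 targets are equal and the O2 targets differ by 10 mm Hg between groups. That is the only contrast in O2 at fixed CO2, and it is wholly confounded with being a diver or a control, which is the comparison of interest.

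**Step 4: what a slope on O2 would carry.** CO2 rise per mm Hg fall in O2, baseline to stage 2:

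- Divers: (57.5 - 35) / (100 - 35) = 22.5 / 65 = 0.346.
- Controls: (57.5 - 35) / (100 - 45) = 22.5 / 55 = 0.409.

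Suppose the response is linear and physiology is identical in both groups, with a CO2 effect per mm Hg equal to k times the O2 effect. The least-squares slope on the O2 fall is then proportional to 1 + k·b, where b is the least-squares slope of CO2 on the O2 fall over the three midpoints: 741.67 / 2216.67 = 0.3346 in divers and 625.0 / 1550 = 0.4032 in controls. The control slope exceeds the diver slope by (1 + 0.4032k) / (1 + 0.3346k) - 1:

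| k (assumed) | Excess in controls |
|---|---|
| 0 | 0% |
| 0.5 | 1.2016 / 1.1673 - 1 = 2.9% |
| 1 | 1.4032 / 1.3346 - 1 = 5.1% |
| 2 | 1.8065 / 1.6692 - 1 = 8.2% |

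The documents give no value for k, so these are illustrations. The direction is that of hypothesis 3a, which expects higher pressure in controls.

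**Step 5: what a comparison by stage would carry.** Controls have O2 targets 10 mm Hg higher than divers at both stages, so the stimulus itself differs between the groups.

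**The case against.** The combined stimulus is deliberate and disclosed. Section A defines the exposure for Objectives 1 and 2 as oxygen and carbon dioxide levels that mimic a breath-hold, Objective 3 repeats those procedures, and Section C names it hypercapnic hypoxia. On this reading, hypoxia is shorthand for the mimic, and the disputed sentence is a follow-on remark in the Introduction. The hypotheses for Objectives 1 to 3 in Section B are not worded as effects of hypoxia alone. All of this stands, and it limits the point to that sentence and to conclusions drawn from it. It does not remove the point, because naming the exposure correctly in the methods does not license a narrower causal conclusion from it.

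A reader might infer that the study cannot answer its main questions. The documents do not support that. Sildenafil against placebo, PFO+ against PFO-, and pressure against IPAVA flow can all be examined under the breath-hold mimic with common gas targets within a group. Objectives 4 and 5 do not use these gas stages. Hypothesis 2b concerns sildenafil's effect on pressure in PFO+ subjects and can be tested without separating the gases. The PFO+ mechanism is already worded as a possibility.

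A reader might also take the correlations to mean that a planned analysis will fail. No regression of pressure on O2 adjusted for CO2 is proposed; the correlations show only that such an adjustment would be a poor rescue. The harm is conditional too: the documents contain no evidence for or against a CO2 response that differs between groups.

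**Conclusion.** The point holds in a limited form. A diver-control difference from this design is a difference in response to combined hypoxia and hypercapnia, and the Section A statement about responses to hypoxia claims more than that. This follows from the absence of any low-O2, resting-CO2 stage and needs no distributional assumption.

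Two further limits apply to the same comparison. By stage, the O2 targets differ between groups by 10 mm Hg. By slope on O2, the accompanying CO2 change differs (0.346 against 0.409 mm Hg per mm Hg O2 fall). The slope distortion is modest, 2.9% to 8.2% for the assumed ratios of 0.5 to 2, under linearity and midpoint targets.

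These figures also assume that the CO2 targets in the detailed procedure apply. The Visit 1 overview says divers receive more CO2 than controls, while the detailed procedure gives both groups the same CO2 targets. The two passages contradict each other, and the figures would change if the targets did.

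**What to change.** - In Section A, restate the inference after Objective 3 as a difference in response to combined hypoxia and hypercapnia (the breath-hold mimic).
- In the report, present any attribution to hypoxia alone, including an exaggerated hypoxic constriction in PFO+ subjects, as interpretation that the study does not test.
- Name the variable against which the slopes in the Visit 1 overview are taken, and state the limit: a stage comparison confounds stimulus with group, and a slope on O2 also carries the CO2 change. Switching from slopes to stages would not solve the problem.
- Reconcile the Visit 1 overview with the detailed gas procedure on whether divers and controls have the same CO2 levels.

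The cost is a narrower stated conclusion and a few sentences of text. The restated inference needs no change to procedures and no additional subjects.
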